### **6.6. Dose Modification**

Dose modification of PF-07081532 is not allowed.

## **6.7. Continued Access to Study Intervention After the End of the Study**

No study intervention will be provided to participants at the end of their study participation.

## **6.8. Treatment of Overdose**

For this study, any dose of PF-07081532 greater than **CCI** within a 24-hour time period will be considered an overdose. This dose is projected to result in exposure that will exceed that observed at the NOAEL in the pivotal 9-month toxicology study in monkeys, after accounting for species differences in plasma protein binding.

There is no specific treatment for an overdose.

In the event of an overdose, the investigator/treating physician should:

1. Contact the study medical monitor within 24 hours.
2. Closely monitor the participant for any AEs/SAEs and laboratory abnormalities as medically appropriate and at least until the next scheduled follow-up.
3. Document the quantity of the excess dose as well as the duration of the overdose in the CRF.
4. Overdose is reportable to Pfizer Safety **only when associated with an SAE**.
5. Obtain a blood sample for PK analysis within 3 days from the date of the last dose of study intervention if requested by the study medical monitor (determined on a case-by-case basis).

## **6.9. Prior and Concomitant Therapy**

All concomitant treatments taken during the study must be recorded with indication, daily dose, and start and stop dates of administration. All participants will be questioned about concomitant treatment at each clinic visit.

Treatments taken within 28 days before study intervention dosing on Day 1 will be documented as a prior treatment. Treatments taken after the first dose of study intervention will be documented as concomitant treatments.

Females using hormonal contraceptives or taking hormone replacement therapy are eligible to participate in this study. See [Appendix 4](#) for hormonal contraceptives that are permitted in this study.

Participants on certain medications are *excluded* from the study (see **CCI** for list of prohibited medications **CCI** and [Appendix 10](#) for a list of other prohibited medications).

Sites are encouraged to contact the sponsor should there be questions as to whether a medication is permitted or prohibited.

#### **6.9.1. Participants in Group 1 Only (without Hepatic Impairment)**

In general, participants in Group 1 (without hepatic impairment) will abstain from all concomitant treatments, except for the treatment of AEs. Of note, are the following **restrictions:**

- Acetaminophen/paracetamol may be used at doses of  $\leq 1$  g/day;
- Herbal supplements must be discontinued ***at least 28 days prior*** to Day 1 and until the follow-up contact;
- Limited use of prescription and nonprescription medications that are not believed to affect the overall results of the study may be permitted on **a case-by-case basis after approval** from the sponsor study team.

#### **6.9.2. Participants in Groups 2, 3 & 4 Only (Hepatic Impairment)**

Participants in Groups 2, 3 & 4 (with hepatic impairment) are permitted to be on stable doses of background medications for the management of their concomitant medical condition(s), as long as this is in line with protocol specifications regarding prohibited medications as described above in [Section 6.9](#) and in [Appendix 9](#) and [Appendix 10](#). On a ***case-by-case basis***, with approval from the sponsor, participants receiving fluctuating concomitant medication/treatment may be considered if the underlying disease is under control. **Whenever possible**, attempts must be made to **not** add new medications or alter the doses and regimens of the concomitant medications after enrollment and for the duration of participation in this study, except in circumstances where a change is deemed medically necessary. Any changes must be captured in the CRF.

Participants may receive any permitted background medications according to their stable medication routine at their usual dosing times. This is with the exception of **CCI** [REDACTED]

[REDACTED] which must not be administered within the 8 hours before study intervention dosing or within the 4 hours after study intervention dosing on Day 1. **On Day 1**, the investigator will determine the appropriate time to administer medications that are to be taken on an empty stomach. Otherwise, permitted concomitant medications that may be administered under fed conditions can be taken with breakfast on the morning of Day 1. On all other study days, participants are to receive their background medications at their usual times.

#### **6.9.3. Rescue Medicine**

There is no rescue therapy to reverse AEs observed with PF-07081532; standard medical supportive care must be provided to manage any AEs.

## **7. DISCONTINUATION OF STUDY INTERVENTION AND PARTICIPANT DISCONTINUATION/WITHDRAWAL**

### **7.1. Discontinuation of Study Intervention**

Since this is a single-dose study, this section is not applicable.

### **7.2. Participant Discontinuation/Withdrawal From the Study**

A participant may withdraw from the study at any time at their own request. Reasons for discontinuation from the study include the following: safety, behavioral, compliance or administrative reasons, or if the study is terminated by sponsor.

At the time of discontinuing from the study, if possible, an early discontinuation visit should be conducted. See the [SoA](#) for assessments to be collected at the time of study discontinuation and follow-up and for any further evaluations that need to be completed.

The early discontinuation visit applies only to participants who are enrolled and then are prematurely withdrawn from the study. Participants should be questioned regarding their reason for withdrawal. The participant will be permanently discontinued from the study intervention and the study at that time.

If a participant withdraws from the study, they may request destruction of any remaining samples taken and not tested, and the investigator must document any such requests in the site study records and notify the sponsor accordingly.

If the participant withdraws from the study and also withdraws consent (see [Section 7.2.1](#)) for disclosure of future information, no further evaluations will be performed and no additional data will be collected. The sponsor may retain and continue to use any data collected before such withdrawal of consent.

#### **7.2.1. Withdrawal of Consent**

Participants who request to discontinue receipt of study intervention will remain in the study and must continue to be followed for protocol-specified follow-up procedures. The only exception to this is when a participant specifically withdraws consent for any further contact with them or persons previously authorized by the participant to provide this information. Participants should notify the investigator in writing of the decision to withdraw consent from future follow-up, whenever possible. The withdrawal of consent should be explained in detail in the medical records by the investigator, as to whether the withdrawal is only from further receipt of study intervention or also from study procedures and/or posttreatment study follow-up, and entered on the appropriate CRF page. In the event that vital status (whether the participant is alive or dead) is being measured, publicly available information should be used to determine vital status only as appropriately directed in accordance with local law.

### **7.3. Lost to Follow-up**

A participant will be considered lost to follow-up if the participant repeatedly fails to return for scheduled visits and is unable to be contacted by the study site.

The following actions must be taken if a participant fails to attend a required study visit:

- The site must attempt to contact the participant and reschedule the missed visit as soon as possible. Counsel the participant on the importance of maintaining the assigned visit schedule and ascertain whether the participant wishes to and/or should continue in the study;
- Before a participant is deemed lost to follow-up, the investigator or designee must make every effort to regain contact with the participant (where possible, 3 telephone calls and, if necessary, a certified letter to the participant's last known mailing address or local equivalent methods). These contact attempts should be documented in the participant's medical record;
- Should the participant continue to be unreachable, the participant will be considered to have withdrawn from the study.

## **8. STUDY ASSESSMENTS AND PROCEDURES**

### **8.1. Administrative Procedures**

The investigator (or an appropriate delegate at the investigator site) must obtain a signed and dated ICD before performing any study-specific procedures.

Study procedures and their timing are summarized in the [SoA](#). Protocol waivers or exemptions are not allowed.

Adherence to the study design requirements, including those specified in the [SoA](#), is essential and required for study conduct.

All screening evaluations must be completed and reviewed to confirm that potential participants meet all eligibility criteria. The investigator will maintain a screening log to record details of all participants screened and to confirm eligibility or record reasons for screening failure, as applicable.

Participants will be screened within 28 days prior to administration of the study intervention to confirm that they meet the study population criteria for the study. If the time between screening and dosing exceeds 28 days as a result of unexpected delays (eg, delayed drug shipment), then participants may be rescreened after contact with a sponsor Clinical representative as described in [Section 5.4](#).

Every effort should be made to ensure that protocol-required tests and procedures are completed as described. However, it is anticipated that from time to time there may be circumstances outside the control of the investigator that make it unfeasible to perform the test. In these cases, the investigator must take all steps necessary to ensure the safety and well-being of the participant. When a protocol-required test cannot be performed, the investigator will document the reason for the missed test and any corrective and preventive actions that they have taken to ensure that required processes are adhered to as soon as possible. The study team must be informed of these incidents in a timely manner.

If done around the time of a blood draw, ECGs and vital sign assessments (BP and pulse rate) should be collected before the blood draw. If an IV catheter is utilized for blood sample collections, ECGs and vital sign assessments (BP and pulse rate) should be collected before insertion of the catheter.

For samples being collected and shipped, detailed collection, processing, storage, and shipment instructions and contact information will be provided to the investigator site prior to initiation of the study.

The total blood sampling volume for individual participants in this study is approximately 170 mL. The actual collection times of blood sampling may change. Additional blood samples may be taken for safety assessments at times specified by Pfizer, provided the total volume taken during the study does not exceed 550 mL during any period of 56 consecutive days.

To prepare for study participation, participants will be instructed on the information in the [Lifestyle Considerations](#) and [Concomitant Therapy](#) sections of the protocol.

## **8.2. Efficacy Assessments**

Not applicable.

## **8.3. Safety Assessments**

Planned time points for all safety assessments are provided in the [SoA](#). Unscheduled safety measurements may be obtained at any time during the study to assess any perceived safety issues.

### **8.3.1. Physical Examinations**

A complete physical examination will include, at a minimum, head, ears, eyes, nose, mouth, neck, skin, heart and lung examinations, lymph nodes, and gastrointestinal, musculoskeletal, and neurological systems.

A brief physical examination will include, at a minimum, assessments of general appearance, the respiratory and cardiovascular systems, and participant-reported symptoms.

Physical examinations may be conducted by a physician, trained physician's assistant, or nurse practitioner as acceptable according to local regulation.

Height and weight will also be measured per the [SoA](#) and recorded in the CRF. For measuring weight, a scale with appropriate range and resolution is used and must be placed on a stable, flat surface. Participants must remove shoes, bulky layers of clothing, and jackets so that only light clothing remains. They must also remove the contents of their pockets and remain still during measurement of weight.

Physical examination findings collected during the study will be considered source data and will not be required to be reported, unless otherwise noted. Any untoward physical examination findings that are identified during the active collection period and meet the definition of an AE or SAE ([Appendix 3](#)) must be reported according to the processes in [Sections 8.4.1 to 8.4.3](#).

### **8.3.2. Vital Signs**

#### **8.3.2.1. Blood Pressure and Pulse Rate**

Blood pressure and pulse rate will be measured as defined in the [SoA](#).

- **Single, seated** BP and pulse rate will be measured with the participant's arm supported at the level of the heart, and recorded to the nearest mmHg, following a rest of **≥5 minutes**;
- Same arm (preferably the dominant arm) will be used for BP/pulse rate assessment throughout the study;
- BP/pulse rate assessment should not be taken from the arm with an IV catheter, if placed;
- Participants should be instructed not to speak during BP/pulse rate measurements.

The same properly sized and calibrated BP cuff will be used to measure BP each time. The use of an automated device for measuring BP and pulse rate is acceptable; however, when done manually, pulse rate will be measured in the brachial/radial artery for at least 30 seconds. When the timing of these measurements coincides with a blood collection, BP and pulse rate should be obtained prior to the nominal time of the blood collection.

Additional collection times, or changes to collection times, of BP and pulse rate will be permitted, as necessary, to ensure appropriate collection of safety data.

Any untoward vital sign findings that are identified during the active collection period and meet the definition of an AE or SAE ([Appendix 3](#)) must be reported according to the processes in [Section 8.4.1 to 8.4.3](#).

### 8.3.3. Electrocardiograms

**Supine** standard 12-lead ECGs utilizing limb leads (with a 10-second rhythm strip) should be collected at times specified in the [SoA](#) section of this protocol using an ECG machine that automatically calculates the HR and measures PR interval, QT interval, QTcF, and QRS complex. Alternative lead placement methodology using torso leads (eg, Mason-Likar) should not be used given the potential risk of discrepancies with ECGs acquired using standard limb lead placement. All scheduled ECGs should be performed after the participant has rested quietly for at least 5 minutes in a supine position.

To ensure safety of the participants, a qualified individual at the investigator site will make comparisons to baseline measurements. Additional ECG monitoring will occur if a) a postdose QTcF interval is increased by  $\geq 60$  ms from the baseline **and** is  $> 450$  ms; or b) an absolute QT value is  $\geq 500$  ms for any scheduled ECG. If either of these conditions occurs, then 2 additional ECGs will be collected approximately 2 to 4 minutes apart to confirm the original measurement. If the QTcF values from these repeated ECGs remain above the threshold value, then a single ECG must be repeated at least hourly until QTc values from 2 successive ECGs fall below the threshold value that triggered the repeat measurement.

If a) a postdose QTcF interval remains  $\geq 60$  ms from the baseline **and** is  $> 450$  ms; or b) an absolute QT value is  $\geq 500$  ms for any scheduled ECG for greater than 4 hours (or sooner, at the discretion of the investigator); or c) QTcF value get progressively longer, the participant should undergo continuous ECG monitoring. A cardiologist should be consulted if QTcF values do not return to less than the criteria listed above after 8 hours of monitoring (or sooner, at the discretion of the investigator).

In some cases, it may be appropriate to repeat abnormal ECGs to rule out improper lead placement as contributing to the ECG abnormality. It is important that leads be placed in the same positions each time in order to achieve precise ECG recordings. If a machine-read QTc value is prolonged, as defined above, repeat measurements may not be necessary if a qualified medical provider's interpretation determines that the QTcF values are in the acceptable range.

ECG values of potential clinical concern are listed in [Appendix 8](#).

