**5.2.2. Additional Exclusion Criteria for Group 1 *Only* (without Hepatic Impairment)**

1. Evidence of chronic liver disease including history of hepatitis, hepatitis B, or hepatitis C or evidence of any of the following, as assessed by sponsor approved laboratory, with a single repeat, permitted to assess eligibility, if needed:

- Hepatitis B virus, defined by presence of HBsAg;

**NOTE:** while *not* part of the tests assessed in this study, a previously positive hepatitis B surface antibody result due to vaccination is permissible.

- Hepatitis C infection, defined by presence of HCVAb **and** HCV RNA.

2. History of alcohol abuse or binge drinking and/or any other illicit drug use or dependence within 6 months of screening. Binge drinking is defined as a pattern of 5 (male) and 4 (female) or more alcoholic drinks in about 2 hours. As a general rule, alcohol intake should not exceed 14 units per week (1 unit = 8 ounces (240 mL) beer, 1 ounce (30 mL) of 40% spirit or 3 ounces (90 mL) of wine).
3. Screening ***supine*** 12-lead ECG demonstrating QTcF interval >450 ms or a QRS interval >120 ms. If QTcF exceeds 450 ms, or QRS exceeds 120 ms, the ECG should be repeated 2 more times and the average of the 3 QTcF or QRS values should be used to determine the participant's eligibility.
4. Screening ***seated*** SBP  $\geq$ 140 mm Hg or DBP  $\geq$ 90 mm Hg, following  $\geq$ 5 minutes of seated rest. If SBP is  $\geq$ 140 mm Hg or DBP  $\geq$ 90 mm Hg, the BP assessment should be repeated 2 more times and the average of the 3 BP values should be used to determine eligibility.
5. Use of ***chronic*** prescription medications within 7 days or 5 half-lives (whichever is longer) prior to Day 1, or for prohibited medications, use within the required washout/restriction period provided in [Appendix 9](#) and [Appendix 10](#).

**NOTE:** Use of selected, limited prescription and non-prescription medications may be permitted ***on a case-by-case basis*** after approval from the sponsor (refer to [Section 6.9](#) for details).

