### 9.3.3.1. Electrocardiogram Analyses

Changes from baseline for the ECG parameters HR, QTcF, PR interval, and QRS complex will be summarized by treatment and time. The frequency of uncorrected QT values above 500 ms will be tabulated.

The number (%) of participants with maximum postdose QTcF values and maximum increases from baseline in the following categories will be tabulated by treatment:

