#### Safety QTcF Assessment

Degree of Prolongation	Mild (ms)	Moderate (ms)	Severe (ms)
Absolute value	>450-480	>480-500	>500
Increase from baseline		30-60	>60

CCI

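### Protocol 8.3.3 sets no stand-alone QTcF trigger: with a baseline above 440 ms, a post-dose QTcF of 500 ms or more may require no repeat ECG

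*Protocol*

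**What the plan says.** Protocol 8.3.3 sets two alternative conditions for collecting two confirmatory ECGs.

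- **Limb (a):** post-dose QTcF is up by at least 60 ms from baseline **and** is above 450 ms.
- **Limb (b):** "an absolute QT value is" at or above 500 ms on a scheduled ECG.

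The later steps use corrected intervals:

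- Confirmation: "If the QTcF values from these repeated ECGs remain above the threshold value", single ECGs follow at least hourly.
- Release from hourly ECGs: "until QTc values from 2 successive ECGs fall below the threshold value that triggered the repeat measurement".
- Referral: "A cardiologist should be consulted if QTcF values do not return to less than the criteria listed above" after 8 hours of monitoring.

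The paragraph on continuous monitoring repeats limbs (a) and (b) with a 4-hour duration. It adds a limb (c) for QTcF that keeps lengthening, without an absolute threshold. A later sentence reads: "If a machine-read QTc value is prolonged, as defined above, repeat measurements may not be necessary", provided a qualified provider finds the QTcF acceptable.

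Elsewhere, the table "Safety QTcF Assessment" in Protocol 9.3.3.1 grades QTcF above 500 ms as severe, and Appendix 8 lists it as a possible SAE. Section 9.3.3.1 treats uncorrected QT as a separate quantity: "The frequency of uncorrected QT values above 500 ms will be tabulated".

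**The concern.** The only absolute QTcF figure in the trigger sentence, 450 ms, is joined to the 60 ms rise. The only stand-alone absolute figure, 500 ms, applies to QT. QT cannot simply be read as QTcF, because 8.3.3 lists both as separate machine outputs and 9.3.3.1 calls the 500 ms QT figure uncorrected.

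A participant who starts with a long QTcF can therefore pass 500 ms without a 60 ms rise. If the heart is beating faster than 60 bpm, QT is shorter than QTcF and limb (b) can stay silent too. Protocol 2.3.1 and 2.3.3 report heart-rate increases with this drug, which move QT further below QTcF.

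What is at stake is a mandatory confirmatory tracing in a range that the protocol itself grades as severe. Screening is stricter: for Group 1, "If QTcF exceeds 450 ms, or QRS exceeds 120 ms, the ECG should be repeated 2 more times", with no change-from-baseline condition. The admitted baselines reach into the gap, mainly in the hepatic groups, whose ceiling is 470 ms.

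**Working it through.** There is no sponsor figure to reproduce. The check applies the two limbs as worded.

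**Inputs**
- Limb (a): rise ≥60 ms and QTcF >450 ms; limb (b): QT ≥500 ms (Protocol 8.3.3).
- Fridericia correction (Protocol Appendix 12): QTcF = QT / (60/HR)^(1/3), so QT = QTcF × (60/HR)^(1/3).
- Screening ceilings for QTcF: 450 ms in Group 1 (5.2.2, criterion 3) and 470 ms in Groups 2–4 (5.2.3, criterion 8).
- Mean terminal half-life 17 to 21 h, with up to a 2-fold increase allowed for (4.2).

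**Step 1: when limb (a) misses a QTcF of 500 ms or more.** The 450 ms part is already met, so limb (a) fails only if QTcF < baseline + 60. The missed range is 500 ≤ QTcF < baseline + 60, with width max(0, baseline − 440). At a baseline of 440 ms or lower it is empty.

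**Step 2: when limb (b) also misses.** QT < 500 requires HR > 60 × (QTcF/500)^3.

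| Baseline QTcF (ms) | Missed QTcF, whole ms | Of these, graded severe (>500) | HR needed at the top value |
|---|---|---|---|
| 440 or lower | none | none | – |
| 442 | 500–501 | 501 | >60.4 bpm |
| 445 | 500–504 | 501–504 | >61.5 bpm |
| 450 (Group 1 ceiling) | 500–509 | 501–509 | >63.3 bpm |
| 460 | 500–519 | 501–519 | >67.1 bpm |
| 470 (Groups 2–4 ceiling) | 500–529 | 501–529 | >71.1 bpm |

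At QTcF 500 ms exactly, any rate above 60 bpm is enough.

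**Step 3: examples where neither limb fires**
- Baseline 450, QTcF 509, 64 bpm: rise 59; QT = 509 × (60/64)^(1/3) = 498.2 ms.
- Baseline 460, QTcF 519, 70 bpm: rise 59; QT = 493.0 ms.
- Baseline 470, QTcF 501, 61 bpm: rise 31; QT = 498.2 ms.
- Baseline 470, QTcF 529, 75 bpm: rise 59; QT = 491.1 ms.

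**Step 4: boundary checks where a limb does fire**
- Baseline 440, QTcF 500: rise 60, so limb (a) fires.
- Baseline 470, QTcF 529, 70 bpm: QT = 502.5 ms, so limb (b) fires.

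**Step 5: slow heart rates.** QT 500 ms corresponds to QTcF 470.5 ms at 50 bpm and 485.7 ms at 55 bpm. Limb (b) fires, but the confirmation metric is already below 500 ms. This can be read as a two-step screen, although the text does not say so.

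**Step 6: exposure at the routine post-dose ECG.** As far as the extracted Schedule of Activities can be read, this is at 144 h only, plus early termination. 144/21 = 6.9 and 144/17 = 8.5 half-lives; with a doubled half-life, 144/42 = 3.4 and 144/34 = 4.2.

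**The case against.** **Intent.** The rest of 8.3.3 fits a QTcF threshold of 500 ms, and the sentence on machine-read values assumes that a prolonged QTc has already been defined. On that view this is an editorial slip. That is probably right, but sites act on the trigger sentence, and it says QT.

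**Deliberate choice.** If QT was meant, 9.3.3.1 and SAP 6.2.4 support it as a safety quantity of its own, and replacing it removes a slow-rate trigger. This stands as a cost of the simplest fix. It does not explain why no QTcF value is enough by itself.

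**Safeguards.** A qualified individual must compare each ECG with baseline. Limb (c) covers progressive lengthening. Abnormal ECGs may be repeated, and 8.3 allows unscheduled measurements. Appendix 8 lists new QTcF above 480 ms as a possible AE and recommends alerts. Appendix 3 obliges supplemental measurements when medically indicated or requested by the sponsor. These make it unlikely that such a value goes unexamined, but none requires the two repeats, and limb (c) needs serial tracings.

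**Materiality.** A case needs a high baseline, a rise short of 60 ms, a heart rate above roughly 60 to 71 bpm, and occurrence at 144 h or at early termination. Protocol 2.2.4.1 reports no clinically significant adverse ECG trends in the completed studies. This stands, and it is why the point is minor.

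**QTc in the release rule.** QTcF is the only correction the protocol names, so the meaning there is clear. Changing it tidies the text but does not close the gap.

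**Conclusion.** The concern holds as a minor inconsistency in the wording of a safety rule. As written, the two limbs miss up to 10 whole-millisecond QTcF values at the Group 1 ceiling and 30 at the Groups 2–4 ceiling; 9 and 29 of these are in the protocol's own severe grade. With a baseline of 440 ms or lower, nothing is missed.

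This is not a demonstrated safety gap. The documents do not give the share of participants with a baseline above 440 ms. With about 24 participants and one late routine post-dose ECG, few or no events are expected; an early-termination ECG could fall sooner, at higher exposure. No PK endpoint or conclusion is affected.

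The result rests on reading QT literally. The sizes at the ceilings also assume that the Day 1 pre-dose baseline does not exceed the screening limit, since the ECG exclusions apply at screening.

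**What to change.** **Preferred.** In 8.3.3, change QT to QTcF in limb (b) of both the trigger sentence and the 4-hour sentence, keeping the 500 ms threshold, and change QTc to QTcF in the hourly-release sentence. Limb (b) then fires at every QTcF of 500 ms or more and matches limb (a), the confirmation and referral steps, the 9.3.3.1 grading and Appendix 8. Uncorrected QT above 500 ms can still be tabulated as planned.

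**Trade-off.** A slow-rate tracing with QT at or above 500 ms but QTcF below 500 ms would no longer force two repeats. To keep that trigger, let limb (b) fire on either QT or QTcF at or above 500 ms, and judge confirmation, release and referral on whichever interval triggered.

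**Cost.** The preferred fix is three word changes in one section. The alternative also needs the confirmation, release and referral sentences reworded. Neither adds a procedure, because the ECG machine already reports both intervals. If the change is handled as a design amendment, IRB/EC approval applies (Protocol 10.1.1), so it is best bundled with another amendment.
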